## 5. Inclusion/Exclusion Criteria

a. Inclusion Criteria:

- I. Arm 1: Healthy adult (age  $\geq 18$  years)
- II. Arm 2: Pancreatic cancer patients (age  $\geq 18$  years) currently receive SBRT treatment at JHU
- III. Arm 3: Hepatic cancer patients (age  $\geq 18$  years) currently receive SBRT treatment at JHU

b. Exclusion criteria: Children (age  $< 18$  years) are excluded.

## 6. Drugs/ Substances/ Devices

Probe holder (passive): FISSO surgical arm (FDA approved)

Probe holder (active): active arm with robotic control (developed by JHU robotic lab)

## 7. Study Statistics

a. Analytic plan for primary objectives:

An effective workflow for real time monitoring of abdominal soft-tissue due to respiration using a 4D ultrasound system will be developed through the use of healthy controls. As

described earlier, these controls will provide data for estimating the background reference for abdominal soft tissue. Data collected on controls will be summarized with descriptive statistics. Quantitative analysis of target/organ motion and displacement recorded in 4D real-time ultrasound scan will be carried out to assess both intra- and interfractional variation as described above in the study. This study will help us to ensure delivery of the prescribed target dose while simultaneously minimizing normal tissue damage. We will consider the approach feasible if we are able to successfully complete the procedure and output the associated data for 50% of the study participants. The software will output a motion curve over time. We will calculate the difference between values on the curve and the values from CBCT at the specific time points that CBCT is performed, and summarize the differences using descriptive statistics. A 95% confidence interval for the difference will be reported. These data will be used to evaluate the accuracy of the 4D ultrasound system.

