## **2. Objectives** (include all primary and secondary objectives)

### Primary objectives:

- a. Establish effective workflow for real time monitoring of abdominal soft-tissue motion due to respiration using 4D ultrasound system
- b. Evaluate feasibility of real time motion monitoring of tumor and surrounding organ/tissue during pancreas and liver SBRT treatments using 4D ultrasound system
- c. Evaluate accuracy of the 4D ultrasound motion monitoring system compare to CBCT based intra-fraction motion monitoring during pancreas and liver SBRT treatments

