## **4. Study Procedures**

- a. **Arm 1:** Validate the ultrasound tracking and establish reference range of motion for abdominal soft tissue motion from healthy individuals.

Fifteen healthy volunteers will be enrolled and informed consent obtained per study guidelines as described. A reference ultrasound scan will be conducted on each subject during breath-hold. Subjects will be required to lie in supine position and engaged with ABC; an ultrasound probe will be placed at the abdomen area with minimal pressure applied. Continuous motion monitoring is achieved by acquiring 4D ultrasound images using a motorized 3D ultrasound probe to image the pancreas, liver and other intra-abdominal organs continuously. Several 4D ultrasound scans will be collected during subsequent breath-holds that serve as secondary images. Registration of the reference and secondary ultrasound scans will be performed with automated registration algorithm built-in with the ultrasound system to evaluate abdominal soft-tissues and organs motion. Additional registration of ultrasound images will be performed with Velocity software to evaluate accuracy of automated registration software in the ultrasound system.

- b. **Arm 2:** Monitor the abdominal soft tissue motion of pancreas patients treated with SBRT during the whole course of treatment.

Thirty pancreatic cancer patients receiving SBRT treatment with ABC will be enrolled and informed consent obtained per study guidelines as described. A 4D ultrasound scan will be acquired at the time at simulation and used as a reference ultrasound image for localizing

tracking target. The ultrasound probe will be placed at the abdominal area to monitor the pancreas motion. The probe will remain in place during the CT scan. Patient setup and the ultrasound probe location will be recorded so that the same setup can be reproduced during treatment delivery. The ultrasound probe in the CT image will be contoured and radiation beams that directly pass through the ultrasound probe will be avoided.

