On each treatment day, 4D ultrasound images will be acquired continuously during beam on time to monitor pancreas motion. The system will record all relevant images, but will not be used in clinical decision making. These data will be used to evaluate the magnitude of target motion and dosimetry deviation due to the motion. Intra-fraction CBCT images acquired during treatment will be registered with reference CT images. Organ motion registered by ultrasound will be compared to motion recorded by CBCT and the accuracy of the ultrasound system will be evaluated.

c. **Arm 3:** Monitor the abdominal soft tissue motion of liver patients receiving SBRT treatment with ABC during the whole course of treatment.

Twenty hepatic cancer patients being treated with SBRT treatment will be enrolled and informed consent obtained per study guidelines as described. A 4D ultrasound scan will be acquired at the time at simulation and used as a reference ultrasound image for localizing tracking target. The ultrasound probe will be placed at the abdominal area to monitor the liver motion. The probe will remain in place during the CT scan. Patient setup and the ultrasound probe location will be recorded so that the same setup could be reproduced during treatment delivery. The ultrasound probe in the CT image will be contoured and radiation beams that directly pass through the ultrasound probe will be avoided.

On each treatment day, 4D ultrasound images will be acquired continuously during beam on time to monitor liver motion. The system will record all relevant images, but will not be used in clinical decision making. These data will be used to evaluate the magnitude of target motion and dosimetry deviation due to the motion. Intra-fraction CBCT images acquired during treatment will be registered with reference CT images. Organ motion registered by ultrasound will be compared to motion recorded by CBCT and the accuracy of the ultrasound system will be evaluated.

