**c. Sample size justification:**

The goals of this study are to test the feasibility of the approach and subsequently generate data for describing the accuracy of the 4D ultrasound motion monitoring system during pancreas and liver SBRT treatments. The variability of the data obtained is currently unknown, so it is difficult to give preliminary estimates of the precision that specific sample sizes will yield. We plan to enroll 15 healthy controls, 30 pancreatic cancer patients, and 20 hepatic cancer patients for generating the pilot data.

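### The single 50% feasibility rule is not split by tumour site, so it can be met with no liver successes, or with only 5 of 30 pancreas successes

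*Combined protocol and SAP*

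**What the plan says.** Section 7a holds the plan's only decision criterion. The approach will be considered "feasible if we are able to successfully complete the procedure and output the associated data for 50% of the study participants". No denominator is given beyond the word participants, and neither patient arm has a minimum.

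The objective that this rule answers is primary objective b in Section 2: "Evaluate feasibility of real time motion monitoring of tumor and surrounding organ/tissue during pancreas and liver SBRT treatments using 4D ultrasound system". It names two sites.

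Section 4 treats the sites as separate arms with different target organs. For Arm 2, "Thirty pancreatic cancer patients receiving SBRT treatment with ABC will be enrolled"; for Arm 3, "Twenty hepatic cancer patients being treated with SBRT treatment will be enrolled". Arm 1 is the volunteer arm: "Fifteen healthy volunteers will be enrolled". Section 7c repeats the numbers: "We plan to enroll 15 healthy controls, 30 pancreatic cancer patients, and 20 hepatic cancer patients for generating the pilot data". No section applies the 50% criterion by arm, and none commits to reporting completion by arm.

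**The concern.** A question about two sites is answered by one undivided proportion. Because the arms differ in size and target organ, success in one can make up for failure in the other. The pancreas arm is large enough to meet a patients-only threshold by itself, and a fully successful liver arm leaves only five pancreas successes to find.

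At stake is the headline conclusion on a primary objective. Someone who follows the plan exactly could report the approach as feasible, and objective b would lead readers to take that as covering both sites, when the procedure had rarely or never been completed at one of them.

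**Working it through.** **Inputs.** Threshold 50% (Section 7a). Arm sizes 15 volunteers, 30 pancreas and 20 liver (Sections 4 and 7c), so 30 + 20 = 50 patients and 15 + 50 = 65 participants. The plan has no sample size, power or error-rate calculation to reproduce. Section 7c says of the data "The variability of the data obtained is currently unknown, so it is difficult to give preliminary estimates of the precision", and the 50% is a chosen criterion.

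**Step 1: turn the rule into a count.** Successes needed = 50% of N, rounded up.
- Patients only, N = 50: 25 needed.
- All participants, N = 65: 32.5, so 33 needed.

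**Step 2: find the lowest passing count at each site.** This is the count needed minus the most that the other arms can supply, and never below zero.
- Patients only: liver 25 − 30 < 0, so 0; pancreas 25 − 20 = 5.
- All participants, with all 15 volunteers successful: 33 − 15 = 18 patient successes suffice (18/50 = 36%). Liver 18 − 30 < 0, so 0; pancreas 18 − 20 < 0, so 0.

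Splits that pass:

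| Denominator | Pancreas | Liver | Volunteers | Total |
|---|---|---|---|---|
| 50 | 25/30 (83.3%) | 0/20 (0%) | not counted | 25/50 = 50% |
| 50 | 5/30 (16.7%) | 20/20 (100%) | not counted | 25/50 = 50% |
| 65 | 18/30 (60%) | 0/20 (0%) | 15/15 | 33/65 = 50.8% |
| 65 | 0/30 (0%) | 18/20 (90%) | 15/15 | 33/65 = 50.8% |

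Exact 95% confidence intervals for the failing arms in the first two rows are 0% to 16.8% for 0/20 and 5.6% to 34.7% for 5/30. Both lie wholly below 50%. If 50% is read as more than 50%, those two rows become 26/30 with 0/20 and 6/30 with 20/20, and the result is the same.

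**Step 3: how often this would happen.** Let X ~ Bin(30, p₁) be pancreas successes and Y ~ Bin(20, p₂) liver successes, independent. The pooled patient rule passes with probability P(X + Y ≥ 25). The separate rules pass with P(X ≥ 15) and P(Y ≥ 10). The documents give no completion rates, so every p below is an assumption, set out as a range.

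| p₁ pancreas | p₂ liver | Pooled ≥25/50 | Pancreas ≥15/30 | Liver ≥10/20 | Both arms |
|---|---|---|---|---|---|
| 0.80 | 0.20 | 0.893 | 1.000 | 0.003 | 0.003 |
| 0.70 | 0.30 | 0.781 | 0.994 | 0.048 | 0.048 |
| 0.30 | 0.90 | 0.811 | 0.017 | 1.000 | 0.017 |
| 0.55 | 0.45 | 0.612 | 0.769 | 0.409 | 0.314 |
| 0.55 | 0.55 | 0.803 | 0.769 | 0.751 | 0.577 |
| 0.60 | 0.60 | 0.943 | 0.903 | 0.873 | 0.788 |
| 0.70 | 0.70 | 0.999 | 0.994 | 0.983 | 0.977 |

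The first three rows show the problem: the pooled rule usually passes although one site is well below 50%. The last three show what a separate rule costs when both sites exceed 50%.

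**The case against.** The strongest objections concern framing and size.

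- **Denominator.** Read literally, the rule covers 65 people, so the 5-of-30 minimum and all the probabilities rest on a patients-only denominator that the plan never states. That is correct and should be said. It does not help the plan: with successful volunteers counted, the pancreas minimum falls from 5 to 0.
- **Wording.** The rule declares the approach feasible and does not mention each site; pooling is inferred from a single undivided threshold. The inference is the natural one, since objective b names both sites and no per-arm reading appears anywhere. At the least, the rule is ambiguous.
- **Visibility.** With no liver successes there would be no liver motion curves to compare with CBCT, so total failure would be hard to overlook. This softens the extreme case. It does not cover a site at 20% or 30%, and the plan does not promise completion or accuracy results by arm.
- **Choice of scenarios.** The contrast depends on how far the sites differ. At 55% and 45% the pooled rule passes with probability 0.61 and the liver rule with 0.41, a much smaller gap. The documents do not say how similar the sites are. The boundary splits need no assumption about rates.
- **Cost of splitting.** This stands. At 60% in both arms, at least one arm misses with probability 1 − 0.788 = 0.21; at 55%, 1 − 0.577 = 0.42. A miss at one site would not, however, cancel a favourable finding at the other.
- **Stakes.** This is a pilot, the ultrasound data do not guide treatment, and no further action is tied to the verdict. That limits the severity, but feasibility is still the first goal named in Section 7c.

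**Conclusion.** The concern holds. As written, the criterion can be satisfied with 0/20 liver successes or, counting patients only, with 5/30 pancreas successes. Both follow directly from the planned arm sizes, reading 50% as at least 50%. Under assumed true rates of 70% and 30%, or 30% and 90% (pancreas and liver), the pooled patient rule passes with probability 0.78 or 0.81, while the weaker site would pass its own 50% rule with probability 0.05 or 0.02. Those probabilities rest on the patients-only denominator, independent patients and illustrative rates. The direction of the problem does not depend on the choice of denominator.

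This should be corrected. It affects the conclusion on a primary objective, but it does not compromise the data, and no stated error rate is wrong because the plan gives none.

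**What to change.** In Section 7a, apply the existing 50% criterion separately to each patient arm: at least 15 of 30 in Arm 2 for pancreas and at least 10 of 20 in Arm 3 for liver. State that each denominator is that arm's patients, draw the feasibility conclusion per site, and report each completion proportion with an exact 95% confidence interval. Give the pooled proportion as description only.

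This is about one sentence of text and needs no added patients, data or procedures. There are two costs. Per-site precision is limited: exactly 50% gives an exact 95% interval of 31.3% to 68.7% for 15/30 and 27.2% to 72.8% for 10/20. One site may also be declared not feasible where the pooled rule would have passed, including by chance when its true rate is only modestly above 50%.

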**Additional Study Investigators:**

[name]  
[name], M.Sc.  
[name] [name]  
[name]  
[name]  
[name] Sc.M.  
[name]  
[name]  
[name], MS

**1. Abstract** (Provide no more than a one page research abstract briefly stating the problem, the research hypothesis, and the importance of the research)

Within the last decade, Linac based stereotactic body radiation therapy (SBRT) has been shown to be an effective treatment option for pancreas and liver tumors. SBRT delivers high doses of radiation therapy to the tumor over only 1-5 treatments. Because of the spatial precision of SBRT, it is feasible to administer a high radiation dose in only a few treatments. By minimizing the amount of radiation to surrounding healthy tissue, it is possible to decrease the rate of toxicity/complication and increase the radiation dose to cancerous tissue, thereby allowing better local control.

SBRT of the abdomen has been limited by the movement of intra-abdominal organs that naturally occurs with respiration and bowel movement. Organ motion occurs both intra- and interfractionally.

While intrafractional motion is a result of respiration, peristalsis and cardiac motion, the magnitude of interfractional target motion is dependent of daily variations in organ filling, weight change, tumor growth and radiation induced changes of tissue. Tumor movement may lead to tumor displacement and suboptimal dose delivery. Accurate localization of the target is very important to improve treatment delivery accuracy and reduce toxicity of the treatment. To evaluate tumor motion due to breathing motion, a 4-D CT simulation scan is performed. If the tumor moves more than 3 mm during a breathing cycle, breathing motion management is employed using Active Breathing Control (ABC) technique. ABC requires the patient to hold his/her breath within the proper tidal volume while treatment is delivered, while free breathing may be resumed between periods of treatment. This technique limits the delivery of RT to specific phases of the respiratory cycle so as to minimize the influence of breathing on the delineated tumor.

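### The 50% feasibility rule pools healthy volunteers with both patient arms and does not say how to score a patient monitored on several treatment days

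*Combined protocol and SAP*

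**What the plan says.** Section 2 lists as primary objective b the feasibility of real-time monitoring of tumor and surrounding tissue during pancreas and liver SBRT. The only numerical criterion for it is in Section 7a: the approach is feasible if the team can "successfully complete the procedure and output the associated data for 50% of the study participants". No arm is named, and success is not defined further.

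Section 7c gives the numbers: "We plan to enroll 15 healthy controls, 30 pancreatic cancer patients, and 20 hepatic cancer patients for generating the pilot data". It derives no sample size from the 50% figure and says the variability of the data is unknown.

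In the patient arms the procedure is repeated. Section 4 says for Arm 2, "On each treatment day, 4D ultrasound images will be acquired continuously during beam on time to monitor pancreas motion", and for Arm 3, "On each treatment day, 4D ultrasound images will be acquired continuously during beam on time to monitor liver motion". The stated aim of Arm 2 is to "Monitor the abdominal soft tissue motion of pancreas patients treated with SBRT during the whole course of treatment", and Arm 3 has the matching aim for liver patients. The Abstract describes SBRT in general: "SBRT delivers high doses of radiation therapy to the tumor over only 1-5 treatments". Neither arm is given its own fraction number.

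Volunteers have a reference scan, and then "Several 4D ultrasound scans will be collected during subsequent breath-holds that serve as secondary images". No repeat visit is described, so a single session is a reasonable inference, but the text does not state it. The Abstract explains that volunteers breathe more regularly, hold their breath longer and show clearer landmarks, whereas abnormal anatomy in patients may produce artifacts that reduce tracking accuracy.

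**The concern.** There are two gaps between the rule and the objective it serves.

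**Who is counted.** The volunteers are there to validate the system and develop the workflow. They have no treatment beam, and Section 4 describes no CBCT for them. By the plan's own account they are easier to scan. If they are in the denominator, their successes can make up for failures in the patients whom objective b is about, and one patient arm can make up for the other.

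**What counts as success.** A patient with several treatment days may have usable tracking on some and not on others. Section 7a does not say whether such a patient is a success. Requiring all days, any one day, or some minimum share can lead to opposite verdicts on the same data. While this is open, the definition could be chosen after the results are known.

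At stake is whether a declaration of feasibility, or its absence, says anything clear about monitoring during pancreatic or liver treatment.

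**Working it through.** **1. The rule read literally (enrolment from Section 7c).**

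- Participants: 15 + 30 + 20 = 65. Half is 32.5, so 33 successes are needed.
- If all 15 volunteers succeed: 33 − 15 = 18 patients are needed, and 18/50 = 36%.
- If all volunteers and all liver patients succeed: 15 + 20 = 35, which already exceeds 33 with no pancreatic success. Since 33 − 15 = 18, 18 of the 20 liver patients would be enough.
- If the rule were meant for patients only, 25 of 50 would be needed. With all 20 liver patients successful, 25 − 20 = 5 of 30 pancreatic patients (17%) would do.

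**2. The missing definition.** The documents give no success rate and no correlation, so every p and ρ here is an assumption. Let p be the chance of success in one fraction, k the number of fractions and ρ the within-patient correlation (beta-binomial model). Then

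P(all k succeed) = product over j = 0 to k−1 of [p(1−ρ) + jρ] / [(1−ρ) + jρ].

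With p = 0.70 and ρ = 0.3 the factors are 0.49/0.70, 0.79/1.00, 1.09/1.30, 1.39/1.60 and 1.69/1.90. The share of patients succeeding is 0.700, 0.464 and 0.358 for k = 1, 3 and 5.

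For p = 0.30 with any one day enough, symmetry gives one minus the chance that all fail: 0.300, 0.536 and 0.642.

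The chance of passing in 30 patients is the binomial probability of at least 15 successes:

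| Definition and assumed p (ρ = 0.3) | k = 1 | k = 3 | k = 5 |
|---|---|---|---|
| All days, p = 0.70 | 0.99 | 0.41 | 0.08 |
| Any day, p = 0.30 | 0.02 | 0.72 | 0.96 |
| At least half, p = 0.70 | 0.99 | >0.99 | >0.99 |
| At least half, p = 0.30 | 0.02 | 0.01 | <0.01 |

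A system working in 70% of fractions can therefore fail the 50% bar, and one working in 30% can pass it. At k = 5 and p = 0.70, changing the definition from all days to at least half moves the chance of passing from 0.08 to above 0.99.

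**3. Sensitivity.**

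- *Stronger correlation, ρ = 0.5 (30 patients):* all days at p = 0.70 gives 0.99, 0.72 and 0.42. Any day at p = 0.30 gives 0.02, 0.42 and 0.71.
- *Pooled rule (33 of 65), ρ = 0.3, each volunteer succeeding once with probability p, both arms at the same k:* all days at p = 0.70 gives >0.99, 0.62 and 0.14. Any day at p = 0.30 gives <0.01, 0.38 and 0.86. The pattern is the same.
- *High reliability, p = 0.90, all days, k = 5:* the pooled rule passes with probability 0.998 even with independent fractions. For 30 patients alone the figure is 0.88 with independent fractions and 0.998 at ρ = 0.3.
- *At least half, p = 0.60, independent fractions, 30 patients:* 0.90, 0.97 and 0.99 for k = 1, 3 and 5.

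**The case against.** The strongest reply is that this is a missing sentence and not a flawed rule. The patient arms are meant to follow motion over the whole course, and Sections 7a and 7b ask for interfractional variation and for dose deviation across treatment. Those results need usable data from most of a patient's fractions, so counting patients is a sensible choice. A participant-level definition such as at least half of the fractions keeps that unit and largely removes the dependence on fraction number. This stands. A reader might infer that the participant is simply the wrong unit, but the documents do not support that.

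It can also be said that the range of 1 to 5 describes SBRT in general. If patients within an arm mostly receive the same number of fractions, they do not face unequal tests. That is fair, but the choice of definition still decides the verdict at any single fraction number above one.

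Failures are probably correlated within patients, since the Abstract names patient-level causes such as implants and fibrosis. For that reason the main figures use a correlation of 0.3 and not independence.

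The sponsor may also have meant patients only, since Section 7a calls the volunteers controls. The text does not say so, and that reading still lets one patient arm carry the other.

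Finally, this is a pilot and the ultrasound does not guide clinical decisions. That limits the harm of a wrong verdict, but the sponsor chose to set a bar, and it should be possible to score it.

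**Conclusion.** The concern holds in two parts. The first needs only the planned enrolment: read literally, the rule can be met with 36% of patients, or with no pancreatic success, so passing it does not establish feasibility in either treated group. The second is that scoring is undefined when a patient has several treatment days. Its size rests on assumed reliability and correlation: in the cases shown, the chance of passing runs from 0.99 down to 0.08, or from 0.02 up to 0.96, as fractions go from 1 to 5.

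Two stronger conclusions are tempting. One is that the plan requires every treatment day to succeed; Section 7a does not say this. The other is that fraction number will drive the verdict whatever definition is adopted. It will not: the effect is small under an at-least-half definition, small at about 90% reliability or above, and weaker as within-patient correlation rises. The plan should be amended before data are seen, but this does not undermine the study's design.

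**What to change.** In Section 7a:

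1. Apply the 50% bar to Arm 2 and Arm 3 separately. Report volunteers descriptively, under the workflow objective.
2. Define success for a fraction: the ultrasound motion curve covers beam-on time and gives a value at the CBCT time point or points. Count missed or abandoned scans as failures.
3. Report the proportion of all delivered fractions that succeed, with a 95% confidence interval clustered by patient.
4. Beside it, report the proportion of patients who succeed under a stated definition, for example at least half of their fractions.
5. State, before data are seen, which of these two proportions the 50% bar applies to.

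The cost is wording and a clustered interval; the data are already to be collected. The main downside is smaller denominators. Near 50%, the half-width for a proportion of patients is 1.96 × √(0.25/n): about 12 points for 65 participants, 18 for 30 and 22 for 20. A fraction-level interval must allow for correlation. With 5 fractions and an assumed correlation of 0.3, the design effect is 1 + 4 × 0.3 = 2.2. The half-width is then 1.96 × √(0.25 × 2.2/150), about 12 points, for 30 patients, and with 100 fractions about 15 points for 20 patients. Counting fractions also gives more weight to patients with more of them, which is another reason to show both proportions.

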The first arm of this study is designed to validate the accuracy and stability of the ultrasound system and establish an efficient workflow to be applied for cancer patients. Healthy volunteers are able to perform more regular breathing patterns and longer breath-holds. Scanning healthy volunteers allows more predictable data acquisition time point and opportunity to develop a general workflow that can be continuously optimized for patient scanning. Anatomical abnormalities (surgical implant, fibrosis and metastases) in patients might produce artifacts in ultrasound images that can reduce motion tracking accuracy. Ultrasound of healthy volunteer with better anatomical landmark visualization helps us to evaluate the stability and accuracy of the ultrasound system and registration software.

For patient study, organ motion registered by ultrasound will be compared to motion recorded by CBCT and the accuracy of the ultrasound system will be evaluated. In addition, imaging and setup efficiency, cost and volume acquisition rate will be compared between CBCT based and 4D ultrasound based intra-fraction motion monitoring.

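### Does the ultrasound-versus-CBCT accuracy analysis need a planned count of CBCTs that have no ultrasound value?

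*Combined protocol and SAP*

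**What the plan says.** Primary objective c in section 2 is to "Evaluate accuracy of the 4D ultrasound motion monitoring system compare to CBCT based intra-fraction motion monitoring during pancreas and liver SBRT treatments". Section 7a gives one analysis for it: "We will calculate the difference between values on the curve and the values from CBCT at the specific time points that CBCT is performed", summarised with descriptive statistics and a 95% confidence interval. The same section calls the approach feasible if the team can "successfully complete the procedure and output the associated data for 50% of the study participants".

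Section 4 sets the ultrasound recording. For Arm 2, "4D ultrasound images will be acquired continuously during beam on time to monitor pancreas motion"; for Arm 3, "4D ultrasound images will be acquired continuously during beam on time to monitor liver motion". For both, "The system will record all relevant images, but will not be used in clinical decision making". Intra-fraction CBCTs are taken in the course of treatment and registered to the reference CT. Arm 1 has no CBCT. Its comparison is of ultrasound with ultrasound: "Registration of the reference and secondary ultrasound scans will be performed with automated registration algorithm built-in with the ultrasound system", with a second software package as a check.

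The Abstract (section 1) warns: "Anatomical abnormalities (surgical implant, fibrosis and metastases) in patients might produce artifacts in ultrasound images that can reduce motion tracking accuracy". Section 7c plans 15 volunteers, 30 pancreatic and 20 hepatic patients. It says that the variability is unknown, and it presents the goals as feasibility first and a description of accuracy after that.

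**The concern.** The accuracy estimate is conditional on having a pair. If the patients who are hard to image are also the ones who yield no usable curve, they drop out of the mean difference and the system looks better than it is. The Abstract names a mechanism that could make this happen, and the 50% rule shows that the investigators would tolerate frequent failure. Yet no section asks how many CBCTs lack a partner, or why, or says that the result describes only the pairs obtained.

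Two features sharpen the worry. Volunteers can help to satisfy the feasibility rule without contributing any CBCT. And the recording window named in section 4 is beam-on time, with no explicit instruction to record through each CBCT. At stake is how far a reader can generalise the only planned comparison with CBCT.

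**Working it through.** The plan gives no standard deviation, margin, power or number of CBCTs per patient, so it has no precision figure to reproduce. What can be checked is how far the 50% rule could thin the pairs, and what that would do.

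**Inputs.** 15 + 30 + 20 = 65 participants, of whom 50 are patients (section 7c); 50% threshold and 95% interval (section 7a). Assumption: one mean difference per patient, since section 7a does not fix the unit of analysis.

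**Step 1: patients left at the limit of the rule.** Section 7a does not say whether the rule is pooled or per arm.
- Per arm: 0.5 × 30 = 15 and 0.5 × 20 = 10, so 25 of 50 patients.
- Pooled: 0.5 × 65 = 32.5, so 33 are needed. If all 15 volunteers succeed, 33 − 15 = 18 of 50 patients (36%) are enough, leaving 32 of 50 (64%) without output.

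**Step 2: width of the interval.** Half-width in SD units = t(0.975, n − 1)/√n.

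| Group | Full n | Half-width | Reduced n | Half-width | Ratio |
|---|---|---|---|---|---|
| Pancreas | 30 | 0.373 | 15 | 0.554 | 1.48 |
| Liver | 20 | 0.468 | 10 | 0.715 | 1.53 |
| Both, per-arm limit | 50 | 0.284 | 25 | 0.413 | 1.45 |
| Both, pooled limit | 50 | 0.284 | 18 | 0.497 | 1.75 |

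These rows assume that the rule is only just met and that every failed participant has no pair at all. The rule does not imply the second condition. It counts participants, whereas pairing happens CBCT by CBCT, so a failed participant may have some pairs and a successful one may lack some. Any widening would also appear in the reported interval, so it is not a hidden loss.

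**Step 3: shift in the mean.** If a share f of patients had no pair and their difference would have been g mm away from the rest, the mean would move by f × g. With assumed gaps of 1 to 3 mm this is 0.5 to 1.5 mm at f = 0.5, and 0.64 to 1.92 mm at f = 0.64. The documents supply no g. The formula also needs an ultrasound-minus-CBCT difference that existed and went unseen. Where tracking was lost or no image was usable, there was no ultrasound value and so no difference to miss. That is a feasibility failure, which section 7a assesses separately. The formula fits best where ultrasound could have tracked but was not recorded.

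**Step 4: is recording at CBCT times in doubt?** Section 4 names beam-on time but also has the system keep all relevant images. The Abstract describes continuous acquisition throughout treatment, and section 7a reads values off the curve at CBCT times. Taken together these presuppose a running curve when a CBCT is made. Nothing in the documents shows that a pair would be lost for this reason.

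**Step 5: does the artifact warning predict missing output?** It speaks of reduced tracking accuracy. A curve that is present but poor stays in the analysis and enlarges the observed differences. The step from poor tracking to absent output is an inference.

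**Step 6: what will be counted anyway.** The 50% rule cannot be evaluated without a count of participants with output, so completeness by participant is already a primary result. The number of pairs is a routine part of a descriptive summary. What remains unrequested is the total of CBCTs acquired and the reasons for gaps.

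**The case for a change.** The strongest reply is that a participant count is not a CBCT count. A patient recorded as a success may still have several unpaired CBCTs, and the feasibility result would not show it. A pooled rule could be met largely through volunteers, who say nothing about CBCT agreement. Reasons for missing values are easiest to note on the treatment day. A tally by arm costs almost nothing and is itself a descriptive statistic, well suited to a pilot.

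Much of this stands. No section asks for that denominator, and a good report would give CBCTs acquired and paired, by arm, and say that the result describes the pairs obtained. But this is a matter of sensible reporting. The tally would correct nothing and would not change the planned difference or its interval. An explicit instruction to record through each CBCT would only write down what the accuracy analysis already takes for granted.

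**Conclusion.** The observation is accurate, but it does not call for a change. The plan omits a reporting detail, most of which its own feasibility count and descriptive summaries supply, and a competent analyst would add the rest. Section 7c places accuracy after feasibility, so describing agreement in the data that usable tracking yields matches the stated purpose.

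The extreme case, an interval 1.45 to 1.75 times as wide, depends on the rule being only just met, on total loss of pairs in every failed participant, on one mean per patient and, for the upper figure, on success in all 15 volunteers under a pooled rule. It is a limit and not a forecast. No bias can be sized, because the gap g is unknown and is undefined where ultrasound gave no value. The stakes are also modest: this is a descriptive pilot whose ultrasound output does not guide treatment.
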